7.4.3 Analysis of Secondary Endpoints

The secondary efficacy variables are:

- The change from baseline to week 4, 8, 12, and end of treatment in mean volume voided per micturition,
- Change from baseline to end of treatment in symptom bother and total health related quality of life scores as assessed by OAB-q questionnaire, and
- Change from baseline to end of treatment in PPBC.

The analysis for secondary endpoints will be performed in FAS-I and PPS population.

Change from baseline to end of treatment in mean volume voided

Change from baseline to end of treatment in mean volume voided will be tested using an ANCOVA model. The response variable will be the mean change in mean volume voided from baseline to the end of the study with treatment group, gender, and age group (<75, ≥ 75) as fixed factors and baseline mean volume voided as the covariate in the model. As part of the ANCOVA results, LS means and two-sided 95% CIs for mean changes from baseline within each treatment group will be provided. Differences in LS means between Mirabegron and placebo will be derived together with 95% CIs and p-values.

Sensitivity analysis

As a sensitivity analysis, a non-parametric test will be applied in investigating mean voided volume. Differences in change from baseline to end of treatment in mean volume voided per micturition between Mirabegron and placebo will be analyzed using a stratified rank ANCOVA model. The response variable will be the standardized ranks of the change from baseline to end of treatment in mean volume voided per micturition. Treatment group and gender will be fixed factors in the model while the standardized ranks of the baseline mean

volume voided per micturition will be included as covariate. Age group (<75, \geq 75) will be included as the stratification factor.

Change from baseline in symptom bother and total health related quality of life scores as assessed by OAB-q questionnaire.

Differences in change from baseline of symptom bother and total health related quality of life scores as assessed by OAB-q between Mirabegron and placebo will be analyzed using an ANCOVA model. The response variable will be the change from baseline in symptom bother and total health related quality of life scores. Treatment group, gender, and age group (<75, \geq 75) will be fixed factors in the model and baseline score will be included as covariates. As part of the ANCOVA results, LS means and two-sided 95% CIs for mean changes from baseline within each treatment group will be provided.

Change from Baseline in PPBC

Differences in change from baseline of PPBC between Mirabegron and placebo will be analyzed using an ANCOVA model. The response variable will be the change from baseline in PPBC. Treatment group, gender and age group (<75, \geq 75) will be fixed factors in the model while the baseline scores will be included as covariates. As part of the ANCOVA results, LS means and two-sided 95% CIs for mean changes from baseline within each treatment group will be provided.

Responder Analysis for OAB-q and PPBC

A responder analysis will be performed for OAB-q at Week 12 or EoT using a logistic regression model. This will be based on the change in OAB-q from baseline. The definition of the categories of the response variable is based on the results of the OAB-q study by Coyne et al, 2007. The responder groups will be defined as follows: A responder is a subject with a minimally important difference (MID) of a 10-point improvement in OAB-q while a non-responder will be a subject with a MID of a less than 10-point improvement in OAB-q.

Two responder analyses will be performed for PPBC at Week 12 or EoT using a logistic regression. One analysis will look at symptom bother and another will look at HRQL total. The logistic regression models will be fitted with binary response variables that are based on change from baseline in PPBC. The response variables will be categorized as follows:

- Improvement: \geq 1 point improvement from baseline to post-baseline for PPBC
- Major improvement: \geq 2 point improvement from baseline to post-baseline for PPBC

The final responder analysis will examine the response outcome defined as zero incontinence episodes post baseline.

Logistic regression for all the responder analyses will include treatment group, age group, gender and baseline measurements as the explanatory variables.

Poisson (Negative Binomial) Regression for Count Variables

Other secondary variables including the number of incontinence episodes, number of urgency incontinence episodes, number of nocturia episodes and number of pads used will be analyzed using the Mixed Effects Poisson (negative binomial) regression model.

7.4.4 Analysis of Exploratory Endpoints

[REDACTED]

7.4.5 Analysis of Other Variables

The analysis of change from baseline scores (to weeks 4, 8, 12, and EoT) for the following additional efficacy endpoints will be analyzed in the same way as described for the mean number of micturitions (ANCOVA), with the exception of urgency incontinence episodes which will be analyzed using a stratified rank ANCOVA.

- Change from baseline in mean number of urgency episodes (grade 3 and/or 4)/24 hour
- Change from baseline in mean number of urgency incontinence episodes/24 hour
- Change from baseline in mean level of urgency
- Change from baseline in mean number of pads
- Change from baseline in mean number of nocturia episodes/24 hour
- Change from baseline in OAB-q subscale scores
- Change from baseline in TS-VAS
- Change from baseline in UAB-LSA
- Change from baseline in VES-13.

7.5 Analysis of Safety

Safety analysis will be performed for adverse events (AEs) and vital signs using the SAF. No inferential comparison between treatment groups will be performed for the safety analysis in this study with the exception of the change from baseline in Montreal Cognitive Assessment (MoCA).

7.5.1 Adverse Events

Summaries and listings of serious adverse events (SAEs) and Serious TEAEs include SAEs upgraded by the sponsor based on review of the Sponsor's list of 'Always Serious' terms if any upgrade was done.

Adverse events will be coded using the Medical Dictionary for Regulatory Activities (MedDRA). The number and percentage of AEs, SAEs, AEs leading to discontinuation, and AEs related to study drug will be summarized by system organ class, preferred term and treatment group. The number and percentage of AEs by severity will also be summarized. All AEs will be listed.

The number and percentage of TEAEs, serious TEAEs, and discontinuations due to a TEAE will be summarized by System Organ Class, Preferred Term, and treatment group. In addition, TEAEs will be summarized by relationship to study drug as determined by the Investigator and by severity for each treatment group.

An overview table will include the following details:

- Number of TEAEs,
- Number and percentage of subjects with TEAEs,
- Number of drug related TEAEs,
- Number and percentage of subjects with causally drug related TEAEs,
- Number of serious TEAEs,
- Number and percentage of subjects with serious TEAEs,
- Number of serious drug related TEAEs,
- Number and percentage of subjects with serious drug related TEAEs,
- Number of TEAEs leading to permanent discontinuation of study drug,
- Number and percentage of subjects with TEAEs leading to permanent discontinuation of study drug, and
- Number of deaths.

The number and percentage of subjects with TEAEs, as classified by SOC and PT will be summarized for each treatment group. Summaries will be provided for:

- TEAEs
- Common TEAEs ($\geq 2\%$ in one group)
- drug related TEAEs,
- severe TEAEs
- serious TEAEs,
- drug related serious TEAEs,
- TEAEs leading to permanent discontinuation of study drug,
- drug related TEAEs leading to permanent discontinuation of study drug,
- Non-serious TEAEs over 5% in any one treatment group

- TEAE by titration doses (prior to titration)
- TEAE by titration doses (post-titration)

The number and percentage of subjects with TEAEs, as classified by PT only, will be summarized for each treatment group and by the subgroups of interest found in Section 7.8.

The number of TEAEs and the number and percentage of subjects with TEAEs, as classified by SOC and PT will also be summarized by severity. In the subject count, if a subject has multiple TEAEs with the same SOC or PT, but with differing severity, then the subject will be counted only once with the worst severity, however, if any of the severity values are missing then the subject will be counted only once with missing severity. In the adverse event count, the adverse events will be presented in each category to which they were classified. Drug related severe TEAEs will be presented in a similar way.

Additional summaries will be provided for the following AEs of special interest:

- Cardiovascular events
- Vital signs (systolic and diastolic blood pressure and pulse rate)
- MI
- Stroke
- Serious Arrhythmias
- Urinary Tract Infection (UTI)
- Acute urinary retention
- Benign prostatic obstruction (BPO) requiring surgery

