6.2 Safety Variables

Safety will be assessed by evaluation of the following variables:

- Treatment-emergent adverse events (TEAEs; frequency, severity, seriousness, and relationship to study drug).
- Adverse Events of Possible Hepatic Origin (See [Appendix 1](#))
- Acute Urinary Retention
- Urinary Tract Infections
- Clinical laboratory variables (hematology, biochemistry including liver function tests, and urinalysis)
- Cardiovascular events, vital signs (systolic and diastolic blood pressure and pulse rate), MI, Stroke and serious arrhythmias.
- Montreal Cognitive Assessment (See [Appendix 5](#))
- Physical Examination
- 12-lead electrocardiogram (ECG)
- Post-Void Residual Volume

TEAE is defined as an adverse event observed after starting administration of the test drug/comparative drug. If the adverse event occurs on Day 1 and the onset check box is marked “Onset after first dose of study drug” or the onset check box is left blank, then the adverse event will be considered treatment emergent. If the adverse event occurs on Day 1 and the onset check box is marked “Onset before first dose of study drug”, then the adverse event will not be considered treatment emergent. If a subject experiences an event both during the pre-investigational period and during the investigational period, the event will be considered as a TEAE only if it has worsened in severity (i.e. it is reported with a new start date). All adverse events collected that begin within 30 days after taking the last dose of study drug will also be counted as TEAEs.

A drug-related TEAE is defined as any TEAE with possible or probable relationship to study treatment as assessed by the investigator or with missing assessment of the causal relationship.

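### In the subject count of the TEAE severity summary, one ungraded event moves a subject with a known severe event in the same SOC or PT to missing severity, so the number of subjects with severe TEAEs can be understated

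*SAP*

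**What the plan says.** SAP 7.5.1 plans a severity summary with two kinds of count: "The number of TEAEs and the number and percentage of subjects with TEAEs, as classified by SOC and PT will also be summarized by severity".

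- **Subject count.** If a subject's TEAEs within one SOC or PT differ in severity, "then the subject will be counted only once with the worst severity". An override follows: "if any of the severity values are missing then the subject will be counted only once with missing severity".
- **Event count.** This has no override: "In the adverse event count, the adverse events will be presented in each category to which they were classified".
- **Drug-related severe events.** "Drug related severe TEAEs will be presented in a similar way".

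The same section plans other outputs on severity. One is a set of subject-level summaries, "The number and percentage of subjects with TEAEs, as classified by SOC and PT will be summarized for each treatment group. Summaries will be provided", and the list that follows includes severe TEAEs. It also states that "All AEs will be listed".

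Protocol 5.5.4 sets the scale: mild, moderate and severe, with nothing above severe. SAP 6.2 shows how the plan treats a different missing assessment. A TEAE counts as drug-related if the investigator calls the relationship possible or probable, "or with missing assessment of the causal relationship".

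**The concern.** A worst-grade count should lose information only when the worst grade is unknown. For a subject who already has an event graded severe, it is known: an ungraded event in the same SOC or PT could be mild, moderate or severe, and the maximum stays severe. The override discards that grade. In the severe category of the subject count the error can go only one way, because subjects can leave that category under the override and none can enter.

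The rule also runs against the SAP's other conventions. Missing causality is resolved cautiously (SAP 6.2), liver tests use the subject's highest value (SAP 7.5.2.1), and same-day ties in categorical variables take the worst value (SAP 7.10.3). In the drug-related severe presentation the two conventions meet: a missing causality brings an event in, while a missing grade may take the subject out of severe.

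Safety and tolerability are the secondary objective (SAP 3.1.2). AEs get no inferential comparison (SAP 7.5), so the descriptive tables are the evidence. The number and percentage of subjects with a severe event is the main thing most readers take from a severity table.

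**Working it through.** The plan gives no missing-grade rate and no expected number of severe TEAEs, so there is no figure to reproduce. The check has two parts.

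**1. The rule applied literally.** Take four made-up subjects with these events in one SOC:

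- A: severe, ungraded
- B: severe, mild
- C: mild, ungraded
- D: ungraded

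| Count | Severe | Mild | Missing |
|---|---|---|---|
| Subjects, SAP rule | 1 (B) | 0 | 3 (A, C, D) |
| Subjects, worst known grade | 2 (A, B) | 1 (C) | 1 (D) |
| Subjects, severe kept and otherwise the SAP rule | 2 (A, B) | 0 | 2 (C, D) |
| Events, under any of these rules | 2 | 2 | 3 |

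Subject A is the clear fault. A's worst grade is known to be severe, yet A is shown as missing. The event rows sum to 2 + 2 + 3 = 7 under every rule, so the event count keeps A's severe event.

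The effect also depends on the row. If A's ungraded event has a different PT from the severe one, A becomes missing on the SOC row only and stays severe on the PT row. Both rows change only if the two events share a PT.

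**2. How often a subject would be moved.** Consider a subject with one event graded severe and k other events in the same SOC or PT. Assume that each of the others lacks a grade with probability m, independently. The severe event is graded by definition, so only the k others can trigger the override:

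P(moved) = 1 − (1 − m)^k

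For two other events and assumed m of 1% to 3%:

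- m = 1%: 1 − 0.99² = 1 − 0.9801 = 2.0%
- m = 3%: 1 − 0.97² = 1 − 0.9409 = 5.9%

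A wider range, with both m and k assumed:

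| m | k = 1 | k = 2 | k = 3 |
|---|---|---|---|
| 0% | 0 | 0 | 0 |
| 0.5% | 0.5% | 1.0% | 1.5% |
| 1% | 1.0% | 2.0% | 3.0% |
| 2% | 2.0% | 4.0% | 5.9% |
| 5% | 5.0% | 9.8% | 14.3% |

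The chance rises with k, so the rule bites mainly on SOC rows, where a subject is more likely to have several events.

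**The case against.** The best reply is that little is lost. The event count in the same summary keeps every graded severe event. A PT row changes only when the ungraded event has that PT. A separate subject-level summary of severe TEAEs is planned, and all AEs are listed. Moved subjects are still shown, under missing. Serious TEAEs, discontinuations due to TEAEs and deaths do not use the rule. Protocol 5.5.4 requires a grade and protocol 8.1.1 makes the investigator responsible for complete eCRF data, so few grades should be missing. All of this stands, and it limits the point to the number and percentage of subjects.

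Part of the rule can also be defended. For a subject with {mild, ungraded} or {moderate, ungraded}, the true worst grade is unknown. Missing is then an accurate label, and the worst known grade could understate severity. This stands too. It does not cover {severe, ungraded}, where nothing about the worst grade is unknown.

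A reader might infer two stronger points that the documents do not support:

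- **That the severity summary hides severe events.** It does not, because the override applies to subjects and not to events.
- **That the summary will contradict the separate severe-TEAE summary.** The SAP does not say how the latter treats missing grades. If it includes everyone with a severe event, the two subject counts can differ. If it uses the override, they agree and both can be too low. Disagreement is possible but not shown.

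Lastly, nothing obliges severity to follow the causality convention. The contrast shows an inconsistency of approach, not a breach of a rule.

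**Conclusion.** The point holds for the subject count. A subject with a known severe TEAE is shown as missing severity when another event in the same SOC or PT is ungraded, and no other section reverses this. The number and percentage of subjects with severe TEAEs can be understated and cannot be overstated by this rule. The same may apply to drug-related severe TEAEs, given the wording that ties them to this presentation.

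The size cannot be found from the documents. The 2.0% to 5.9% rests on an assumed missing rate of 1% to 3% per event, two other events in the SOC, and independent missingness. It applies to such subjects only and not to the trial as a whole. The effect is likely to be small, but the count is wrong wherever the rule applies and is easy to correct.

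**What to change.** Replace the override clause in SAP 7.5.1:

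- Count any subject with at least one event graded severe in that SOC or PT as severe. State that this holds for the severity summary and for the severe and drug-related severe TEAE summaries. That also settles how the separate severe summary treats missing grades.
- For other subjects, choose one rule and state it: either the worst known grade, with missing used only when no grade is known, or missing wherever an ungraded event leaves the worst grade truly unknown.

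If the sponsor wants a cautious bound, a sensitivity table could count missing as severe. It should not be the main display, because it would relabel subjects whose known grades are all mild.

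The cost is a sentence or so in the SAP and a small program change. Data collection and the efficacy analyses are untouched.

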7.5.2 Clinical Laboratory Evaluation

Laboratory variables (biochemistry, hematology, and urinalysis) will be descriptively summarized for Screening and Week 12/End of Treatment and change from Screening to End of Treatment will be summarized by treatment group.

Quantitative clinical laboratory variables, i.e. hematology, biochemistry, and urinalysis will be summarized using mean, standard deviation, minimum, maximum, Q1, Q3, and median for each treatment group at each visit. Additionally, a within-subject change will be calculated as the post-baseline measurement minus the baseline measurement and summarized in the same way.

Laboratory results will be classified as low (L), normal (N), or high (H) at each visit according to the laboratory supplied reference ranges. Shift tables of reference range changes from Screening to Week 12/End of Treatment during the double-blind treatment period by treatment group will be summarized for all laboratory values.

Laboratory abnormalities will be evaluated based on the Potentially Clinically Significant (PCS) laboratory criteria. For each laboratory PCS criterion, the number and percent of subjects who have a laboratory value meeting the PCS criteria during the double-blind treatment period will be summarized by treatment group. The directions of changes (high or low) in PCS will be indicated in the tables. The pre-defined criteria for PCS laboratory values are presented below.

Potentially Clinically Significant Laboratory Criteria			
Laboratory Parameter	Unit	Low PCS Criterion	High PCS Criterion
Hematology			
Hemoglobin	g/L	< 80	>180
Hematocrit	Fraction	< 0.25	> 0.55
Erythrocyte (Red Blood Cell Count)	$\times 10^{12}/L$	< 2.5	> 7.0
Platelet Count	$\times 10^9/L$	< 120	> 500
Leukocyte (White Blood Cell Count)	$\times 10^9/L$	< 2.5	> 18
Potassium	Meq/L	< 3.0	> 6.0

7.5.2.1 Liver function tests

The following potentially clinically significant criteria in liver function tests for Alkaline Phosphatase (ALP), Alanine Transaminase (ALT), total bilirubin, Aspartate Transaminase (AST) and their combination are defined. The subject's highest value during the investigational period will be used.

Parameter	Criteria
ALT	> 3xUpper Limit of Normal (ULN) > 5xULN > 10xULN > 20xULN
AST	> 3xULN > 5xULN > 10xULN > 20xULN
ALT or AST	> 3xULN
Total Bilirubin	> 2xULN
ALP	> 1.5xULN
ALT and/or AST AND Total Bilirubin ^(*)	(ALT and/or AST > 3xULN) and total bilirubin > 2xULN

(*) Combination of values measured within same sample

The number and percentage of subjects with potentially clinically significant values in liver function tests during the investigational period will be presented by treatment group.

7.5.3 Vital Signs

The baseline visit is the last measurement taken prior to initial study drug administration.

Pulse rate, systolic blood pressure, and diastolic blood pressure will be summarized by treatment group, by Home Based Blood Pressure Monitoring (HBPM) and office based, and the subgroups of interest found in Section 7.8 using descriptive statistics (mean, standard deviation, minimum, maximum, and median) for baseline value, specified post-baseline time point values (Week 4, Week 8, and Week 12/EoT), and change from baseline to each

specified post-baseline time point. Morning and evening blood pressure will be reported separately. The first reading of HBPM from each time period will be discarded and the subsequent two readings for each time period will be averaged over the 3-day diary. The average change from baseline to end of treatment for each vital sign variable will be analyzed using the ANCOVA model with treatment group and gender as fixed factors and baseline vital sign value as covariate. Age group (<75 , ≥ 75) will be included as the stratification factor. It should be noted that age group was omitted from the description of the analysis in the protocol. As part of the ANCOVA results, LS means and two-sided 95% CIs for mean changes from baseline within each treatment group will be provided. Differences in LS means between mirabegron and placebo will be derived together with 95% Cis.

An AE of hypertension will be recorded if one of the following criteria is met on 2 or more consecutive visits:

1. If the average systolic blood pressure is > 140 mmHg AND/OR the average diastolic blood pressure is > 90 mmHg at two consecutive visits after Baseline (Visit 3) in subjects who were normotensive (average systolic blood pressure < 140 mmHg and average diastolic blood pressure < 90 mmHg [WHO-ISH, 2003]) at Baseline (Visit 3).
2. If the average systolic blood pressure is increased > 20 mmHg AND/OR the average diastolic blood pressure is increased > 10 mmHg at two consecutive visits as compared to Baseline (Visit 3) in subjects with hypertension at Baseline (Visit 3).
3. If treatment with antihypertensive drugs is initiated for treatment of hypertension or if the dose of prior antihypertensive drugs is increased due to an increase in blood pressure.

An AE of "increased" Blood Pressure should be considered if the above conditions are not met, but a high blood pressure is recorded."

An AE of tachycardia should be considered if resting heart frequency (pulse rate) is > 100 bpm.

Tables for potentially clinically significant vital signs will be generated using baseline value and highest value obtained during treatment for each subject for each treatment group. Number and percentage of subjects with more than 10/15/20 mmHg increase from baseline in SBP, more than 5/10/15 mmHg increase in DBP or more than 5/10/15 bpm increase from baseline in pulse rate, on 2 consecutive post-baseline visits will be summarized by treatment group. Number and percentage of subjects with vital sign variables shifting between JNC-7 defined risk categories will be summarized by treatment group. These categories are listed below:

Category	Systolic BP (mm Hg)	Diastolic BP (mm Hg)
Normal	< 120	< 80
Prehypertension	120-139	80-89
Hypertension Stage 1	140-159	90-99
Hypertension Stage 2	≥ 160	≥ 100

Number and percentage of subjects with a PR > 100 bpm at any office visit or by HBPM will be summarized by treatment group separately.

The following Vital Sign data will be presented graphically by treatment group across visits:

- Change from baseline in vital sign results using mean (+/- 95% CI) plot
- Mean qualitative vital sign results using a bar chart
- Scatter plot of maximum vital sign results on treatment versus baseline value (separate plot for SBP, DBP, and pulse).

